7.1 Sample Collection

At Visits 2, 3 and 4, 3 mL of blood will be collected and at Visit 5, 6 mL of blood will be collected in tubes provided by the Sponsor. Immediately prior to the blood draw, the staff member performing the procedure will verify the subject's identity; will verify the assigned subject's number on the pre-printed label that contains that subject's number and the sampling stage; and will attach the label to the tube. Blood is to be taken from the limb opposite to the one that will be used for vaccination.

7.2 Sample Preparation

Detailed instructions on how to prepare blood samples for assessment of immune response are contained in the Operating Guidelines provided to the site. An overview of the procedures is provided here.

Following the blood draw, the tubes are to be left undisturbed, positioned vertically and not shaken, for a minimum of 1 hour and a maximum of 24 hours to allow the blood to clot. Samples can be stored at room temperature for up to 2 hours; beyond 2 hours, they must be refrigerated at a temperature of +2°C to +8°C and must be centrifuged within a maximum of 24 hours.

The samples are then centrifuged, and the serum is transferred to the appropriate number of aliquoting tubes. These tubes must be pre-labeled with adhesive labels that identify the study code, the subject's number and the sampling stage or visit number.

The subject's number and the date of sampling, the number of aliquots obtained, the date and time of preparation, and the subject's consent for future use of his / her samples are to be specified on a sample identification list and recorded in the source document. Space is provided on this list for comments on the quality of samples.

7.3 Sample Storage and Shipment

During storage, serum tubes are to be kept in a freezer whose temperature is set and maintained at -20°C or below. The temperature will be monitored and documented on the appropriate form during the entire study. If it rises above -10°C for any period of time, the Clinical Logistics Coordinator must be notified. See the Operating Guidelines for further details.

Shipments to the laboratories will be made only after appropriate monitoring, and following notification of the Clinical Logistics Coordinator. Sera will be shipped frozen, using dry ice to maintain them in a frozen state, in the packaging container provided by the carrier. Again, temperatures will be monitored. Shipments must be compliant with the United Nations (UN) Class 6.2 specifications and the International Air Transport Association (IATA) 602 packaging instructions.

Samples will be shipped to R&D Global Operations at Sanofi Pasteur. The address is provided in the Operating Guidelines.

Blood samples for the assessment of antibody responses to the study vaccines will be stored for up to 25 years after the end of the study. It can take many years for a vaccine to be developed and approved for use. Even after the vaccine is made available to the public, we continue to gain more knowledge of the vaccine's benefits and risk or improve the methods we use to measure the efficacy of the vaccine. It is for this reason that it is important we retain these blood samples so that we can go back and confirm the results of this study if new information or improved methods become available.

7.4 Future Use of Stored Serum Samples for Research

Any unused part of the serum samples will be securely stored at the Sanofi Pasteur R&D Global Operations for at least 25 years after the last license approval in the relevant market areas has been obtained for the vaccine being tested.

Subjects' parents / legally acceptable representatives will be asked to indicate in the ICF whether they will permit the future use of any unused stored serum samples for other tests. If they refuse permission, the samples will not be used for any testing other than that directly related to this study. If they agree to this use, they will not be paid for giving permission. Anonymity of samples will be ensured. The aim of any possible future research is unknown today, and may not be related to this particular study. It may be to improve the knowledge of vaccines or infectious diseases, or to improve existing tests or develop new tests to assess vaccines. Human genetic tests will never be performed on these samples without specific individual informed consent.

8 Clinical Supplies

Sanofi Pasteur will supply the study sites with protocols, ICFs, SAE reporting forms, diary cards, and other study documents, as well as with the following study materials: investigational and control vaccines, blood collection tubes, cryotubes, cryotube storage boxes, cryotube labels, temperature recorders, shipping containers, rulers, and digital thermometers.

The means for performing Electronic Data Capture (EDC) will be defined by Sanofi Pasteur. If a computer is provided by Sanofi Pasteur, it will be retrieved at the end of the study.

The Investigator will supply all vaccination supplies, phlebotomy, and centrifugation equipment, including biohazard and / or safety supplies. The biohazard and safety supplies include needles and syringes, examination gloves, laboratory coats, sharps disposal containers, and absorbent countertop paper. The site will ensure that all biohazard wastes are autoclaved and disposed of in accordance with local practices. The Investigator will also supply appropriate space in a temperature-monitored refrigerator for the storage of the products and for the blood samples, and appropriate space in a temperature-monitored freezer for serum aliquots.

In the event that additional supplies are required, study staff must contact Sanofi Pasteur, indicating the quantity required. Contact information is provided in the Operating Guidelines.

They must allow approximately 1 week for an order to be filled and to have the supplies sent to their site.

9 Endpoints and Assessment Methods

9.1 Primary Endpoints and Assessment Methods

9.1.1 Safety

There are no primary objectives for safety.

9.1.2 Immunogenicity

9.1.2.1 Immunogenicity Endpoint

The primary endpoint for the evaluation of immunogenicity is:

Antibody titers $\geq 1:8$ against meningococcal serogroups A, C, W, and Y measured by hSBA assessed 30 days after vaccination(s) at 12 to 13 months of age (Group 1 versus Group 2)

9.1.2.2 Immunogenicity Assessment Methods

The hSBA testing will be performed at GCI, Swiftwater, PA.

Antibodies to meningococcal antigens (hSBA Method)

Functional meningococcal antibody activity against serogroups A, C, W, and Y will be measured in hSBA. Two-fold dilutions of test sera are prepared in sterile 96-well microtiter plates. Serogroup-specific meningococcal bacteria along with human complement are added to the serum dilutions and allowed to incubate. After this incubation period, an agar overlay medium is added to the serum/complement/bacteria mixture, allowed to harden, and then incubated overnight at 37°C with 5% carbon dioxide (CO₂). Bacterial colonies present in the wells are then counted. The endpoint titer is determined by the reciprocal serum dilution yielding $\geq 50\%$ killing as compared to the mean of the complement control wells. The lower limit of quantitation (LLOQ) of the hSBA assay is a titer of 1:4.

9.1.3 Efficacy

No clinical efficacy data will be obtained in the study.

9.2 Secondary Endpoints and Assessment Methods

9.2.1 Safety

There are no secondary objectives for safety.

9.2.2 Immunogenicity

9.2.2.1 Immunogenicity Endpoints

- 1) Antibody titers (GMTs) against meningococcal serogroups A, C, W, and Y measured by hSBA 30 days after vaccinations with MenACYW conjugate vaccine concomitantly with Bexsero[®] or alone at 12 to 13 months of age (Group 1 vs Group 2)
- 2) Before and 30 days after the 1st dose of MenACYW conjugate vaccine administered at 3 months of age, before and 30 days after the 2nd dose of MenACYW conjugate vaccine administered at 12 to 13 months of age, the following endpoints against meningococcal serogroups A, C, W, and Y will be assessed using hSBA and rSBA (subset) for Group 1 and Group 2:
 - hSBA and rSBA antibody titer (GMT)
 - titer distribution and RCDC
 - hSBA antibody titer $\geq 1:4$ and titers $\geq 1:8$
 - rSBA antibody titer $\geq 1:8$ and titers $\geq 1:128$
 - antibody titer ≥ 4 -fold rise from pre-vaccination to post-vaccination

- hSBA and rSBA vaccine seroresponse^a
- 3) 30 days after the 1st dose of MenACYW conjugate vaccine administered at 3 months of age, and before the 2nd dose of MenACYW conjugate vaccine administered at 12 to 13 months of age, the following endpoints against meningococcal serogroups A, C, W, and Y will be assessed using hSBA and rSBA (subset) for Group 1 and Group 2 antibody persistence evaluation:
- hSBA and rSBA antibody titer (GMT)
 - hSBA antibody titer $\geq 1:4$ and titers $\geq 1:8$
 - rSBA antibody titer $\geq 1:8$ and titers $\geq 1:128$

9.2.2.2 Immunogenicity Assessment Methods

The immunogenicity assessment methods for the secondary endpoints are the same as those presented in [Section 9.1.2.2](#).

The rSBA testing is planned to take place at the Public Health England, Manchester, UK laboratory of [name]. Only a subset of samples in each group will be tested by rSBA (first 100 subjects randomized to have 3 blood draws in each of the 3 groups).

Antibodies to meningococcal antigens (rSBA Method)

Functional meningococcal antibody activity against serogroups A, C, W, and Y will be measured in rSBA. Two-fold dilutions of test sera are prepared in sterile 96-well microtiter plates. Serogroup-specific meningococcal bacteria along with baby rabbit complement are added to the serum dilutions and allowed to incubate. After this incubation period, an agar overlay medium is added to the serum/complement/bacteria mixture, allowed to harden, and then incubated overnight at 37°C with 5% CO₂. Bacterial colonies present in the wells are then counted. The endpoint titer is determined by the reciprocal serum dilution yielding $\geq 50\%$ killing as compared to the mean of the complement control wells. The LLOQ of the rSBA assay is a titer of 1:4.

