--	---

	
Antibodies to meningococcal serogroups A, C, W, and Y antigens will be measured by serum bactericidal assay using human complement (hSBA) for all subjects providing a blood sample at corresponding time points (Visit 2, Visit 3, Visit 4, and Visit 5), and by serum bactericidal assay using baby rabbit complement (rSBA) for a subset of subjects (the first 100 subjects randomized to have 3 blood draws in each of the 3 groups).
																																																			

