* This call is made 8 days after the respective vaccinations. If day 8 falls on a weekend or holiday, the telephone call may be made on the following business day. During this telephone call, the staff will find out whether the subject experienced any SAE not yet reported and will remind the subject's parent / legally acceptable representative to continue using the diary card, and confirm the date and time of the next visit.

† Visit 4 may occur anytime from the day the subject becomes 12 months of age until the day before becoming 14 months of age.

‡ Routine pediatric vaccines may be given as per standard of care outside of the study, after all visit procedures have been completed.

§ Physical examination should be performed as per standard of care.

** A health assessment will be performed by a study nurse at Visit 4. A physical examination may be performed on the basis of relevant medical history/study nurse health assessment according to the investigator's clinical judgment.

†† Temperature (route as per standard of care) needs to be measured before each vaccination and recorded in the source documents.

‡‡ Should a subject receive oral or injectable antibiotic therapy within 3 days prior to any blood draw, the investigator will postpone that blood draw until it has been 3 days since the subject last received oral or injectable antibiotic therapy. Postponement must still be within the timeframe for blood draw. If postponement would result in the sample collection falling outside of this timeframe, the blood sample should be collected without postponement, and it should be documented appropriately that the sample was taken less than 3 days after stopping antibiotic treatment.

§§ Blood sample will be drawn prior to vaccination.

*** Blood samples will be drawn from ~ 70 randomized subjects only (Subset A).

††† Blood samples will be drawn from ~ 90 randomized subjects only (Subset B).

‡‡‡ A physical examination may be performed on the basis of relevant medical history at the time of the visit according to the investigator's clinical judgment.

§§§ Routine pediatric vaccines: At Visit 1: Infanrix hexa[®], Rotarix[®], Prevenar 13[®]; at Visit 2: Infanrix hexa[®], Rotarix[®]; at Visit 3: Infanrix hexa[®], Prevenar 13[®]

**** The diary card dispensed to the subject's parent/legally acceptable representative at each visit must correspond to the number of injections given at that visit.

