Note: Each visit may be conducted at the site (site visit) or at the subject's home (home visit).

Blood Sampling

Subjects will provide the following blood samples:

- Groups 1 and 2: 160 subjects in each group will be randomized to have 3 blood draws at the intervals mentioned below. The remaining subjects will only have 1 blood draw at Visit 5.
- Group 3: all 160 subjects will have 3 blood draws.

For the subjects randomized to have 3 blood draws in Group 1 and Group 2, the first 2 blood draws will be performed in a staggered way – approximately half of the subjects (~70 subjects in each group) will have blood draws at Visit 2 and Visit 3 (subset A), and the remaining half (~90 subjects in each group) will have blood draws at Visit 3 and Visit 4 (subset B). The third blood draw will be performed at Visit 5 for all subjects.

Subset A (~70 subjects in each group):

- a pre-vaccination blood sample at Visit 2
- a blood sample at Visit 3 (30 days after vaccination at Visit 2)
- a blood sample at Visit 5 (30 days after vaccination at Visit 4)

Subset B (~90 subjects in each group):

- a blood sample at Visit 3 (30 days after vaccination at Visit 2)
- a pre-vaccination blood sample at Visit 4
- a blood sample at Visit 5 (30 days after vaccination at Visit 4)

For the subjects randomized to Group 3, the first 2 blood draws will be performed in a staggered way – approximately half of the subjects (~70 subjects) will have blood draws at Visit 2 and Visit 3 (subset A), and the remaining half (~90 subjects) will have blood draws at Visit 3 and Visit 4 (subset B). The third blood draw will be performed at Visit 5 for all subjects.

Subset A (~70 subjects):

- a pre-vaccination blood sample at Visit 2
- a blood sample at Visit 3 (30 days after vaccination at Visit 2)
- a blood sample at Visit 5 (30 days after vaccination at Visit 4)

Subset B (~90 subjects):

- a blood sample at Visit 3 (30 days after vaccination at Visit 2)
- a pre-vaccination blood sample at Visit 4
- a blood sample at Visit 5 (30 days after vaccination at Visit 4)

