5.1.3 Study Plan

Vaccination and Blood sampling

A schedule of assessments, study vaccinations, and blood draws is provided in the [Tables of Study Procedures](#) and in [Table 5.1](#). Subjects in Group 1 and 2 will have 1 or 3 blood draws. Subjects in Group 3 will have 3 blood draws.

Table 5.1: Schedule of vaccination and blood draws

Group	Visit								
	Visit 1 2 months	Visit 2 3 months		Visit 3 4 months		Visit 4 12 - 13 months		Visit 5 13 - 14 months	
	Vaccinations	Blood collection	Vaccinations	Blood collection	Vaccinations	Blood collection	Vaccination(s)	Blood collection	Vaccinations*
1 (N=320)	Infanrix hexa Rotarix Bexsero PCV13	BL1 (n=70)†	Infanrix hexa Rotarix MenACYW	BL2 (n=70)†	Infanrix hexa Bexsero PCV13		Bexsero MenACYW	BL3 (n=320)	PCV13 Menitorix Priorix/M-M-RVAXPRO
				BL1 (n=90)‡					
2 (N=320)	Infanrix hexa Rotarix Bexsero PCV13	BL1 (n=70)†	Infanrix hexa Rotarix MenACYW	BL2 (n=70)†	Infanrix hexa Bexsero PCV13		MenACYW	BL3 (n=320)	PCV13 Menitorix Bexsero§ Priorix/M-M-RVAXPRO
				BL1 (n=90)‡					
3** (N=160)	Infanrix hexa Rotarix Bexsero PCV13	BL1 (n=70)†	Infanrix hexa Rotarix	BL2 (n=70)†	Infanrix hexa Bexsero PCV13		Bexsero	BL3 (n=160)	PCV13 Menitorix Priorix/M-M-RVAXPRO
				BL1 (n=90)‡					

* Routine vaccines to be given after study visit procedures are completed. No immunogenicity or safety data will be collected after the administration of these vaccines.

†The first ~70 subjects randomized to have 2 blood draws at Visit 2 and Visit 3 (Subset A)

‡The last ~90 subjects randomized to have 2 blood draws at Visit 3 and Visit 4 (Subset B)

§For Group 2, the 3rd dose of Bexsero® will be provided by Sponsor for completion of the Bexsero vaccination series.

**Licensed ACWY conjugate meningococcal vaccine (Nimenrix®) will be offered at least 30 days after the last study visit (Visit 5) at an additional optional visit.

BL: Blood draw prior to vaccination; N: number of subjects randomized in each group; n: number of subjects randomized to have blood draws in each group at the given visit

Collection of safety data

- All subjects will be observed for 30 minutes after each vaccination, and any unsolicited systemic AEs occurring during that time will be recorded as immediate unsolicited systemic AEs in the electronic case report book (CRB).

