- Groups 1 and 2: 160 subjects in each group will be randomized to have 3 blood draws at the intervals mentioned below. The remaining subjects will only have 1 blood draw at Visit 5.
- Group 3: all subjects will have 3 blood draws.

For the subjects randomized to have 3 blood draws in Group 1 and Group 2, the first 2 blood draws will be performed in a staggered way – approximately half of the subjects (~70 subjects in each group) will have blood draws at Visit 2 and Visit 3 (subset A), and the remaining half (~90 subjects in each group) will have blood draws at Visit 3 and Visit 4 (subset B). The third blood draw will be performed at Visit 5 for all subjects.

Subset A (~70 subjects in each group):

- a pre-vaccination blood sample at Visit 2

^a Medication(s) prescribed for preventing AE occurrence (e.g. paracetamol to reduce the risk of fever)

- a blood sample at Visit 3 (30 days after vaccination at Visit 2)
- a blood sample at Visit 5 (30 days after vaccination at Visit 4)

Subset B (~90 subjects in each group):

- a blood sample at Visit 3 (30 days after vaccination at Visit 2)
- a pre-vaccination blood sample at Visit 4
- a blood sample at Visit 5 (30 days after vaccination at Visit 4)

For the subjects randomized to Group 3, the first 2 blood draws will be performed in a staggered way – approximately half of the subjects (~70 subjects) will have blood draws at Visit 2 and Visit 3 (subset A), and the remaining half (~90 subjects) will have blood draws at Visit 3 and Visit 4 (subset B). The third blood draw will be performed at Visit 5 for all subjects.

Subset A (~70 subjects):

- a pre-vaccination blood sample at Visit 2
- a blood sample at Visit 3 (30 days after vaccination at Visit 2)
- a blood sample at Visit 5 (30 days after vaccination at Visit 4)

Subset B (~90 subjects):

- a blood sample at Visit 3 (30 days after vaccination at Visit 2)
- a pre-vaccination blood sample at Visit 4
- a blood sample at Visit 5 (30 days after vaccination at Visit 4)

See the [Table of Study Procedures](#) and [Section 5.1.3](#) for details of the sampling schedule.

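### Does the rule that rSBA is run on the first 100 three-draw subjects leave too few Visit 4 rSBA results?

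*Protocol*

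**What the plan says.** **Who is assayed.** Section 9.2.2.2 restricts rSBA: "Only a subset of samples in each group will be tested by rSBA (first 100 subjects randomized to have 3 blood draws" in each group). The synopsis says the same: "the first 100 subjects randomized to have 3 blood draws in each of the 3 groups".

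**Who is bled when.** Section 5.1.1 and Section 7 state, for Groups 1 and 2, that "160 subjects in each group will be randomized to have 3 blood draws at the intervals mentioned below". All 160 Group 3 subjects have three draws. Subset A (~70 per group) is bled at Visits 2, 3 and 5. Subset B (~90 per group) is bled at Visits 3, 4 and 5. Section 5.1.4 confirms that the Visit 4 sample is taken from Subset B alone.

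**How the subsets are described.** The footnotes to Table 5.1 in Section 5.1.3 use order words: "The first ~70 subjects randomized to have 2 blood draws at Visit 2 and Visit 3 (Subset A") and "The last ~90 subjects randomized to have 2 blood draws at Visit 3 and Visit 4 (Subset B"). The legend of the same table defines n as the "number of subjects randomized to have blood draws in each group at the given visit". The Group 1 procedure table says "Blood samples will be drawn from ~ 90 randomized subjects only (Subset B"), and the Group 2 and 3 tables carry matching footnotes. Section 5.1.1 gives no order: "and the remaining half (~90 subjects in each group) will have blood draws at Visit 3 and Visit 4 (subset B").

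**What uses a Visit 4 rSBA result.** Section 12.1.2.2 needs it for antibody persistence after dose 1 (Secondary Objective 3), and for the pre-dose-2 titers, 4-fold rise and seroresponse around dose 2 (part of Secondary Objective 2). Section 12.1.3 needs it for the Group 3 time point before the toddler Bexsero dose. Both sections state that no hypotheses will be tested.

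**The concern.** Two selection rules use nearly the same phrase. The rSBA set is the first 100 subjects randomized to three draws, and Subset A is the first ~70 subjects randomized to the early draws. If both mean order of entry, the rSBA set takes in the whole of Subset A before it reaches anyone in Subset B. The subset with the only Visit 4 sample, which is the larger subset in the cohort, would then be the smaller part of the rSBA set.

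The reading deserves attention because the visit procedures in Section 5.1.4 send the reader to Sections 5.1.2 and 5.1.3 for the subset definition. Section 5.1.2 does not mention subsets, so Table 5.1 and its footnotes carry the definition. Section 6.5 describes only the 2:2:1 allocation to groups and does not mention A and B.

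At stake would be the precision of the rSBA persistence and dose-2 response estimates. An analysis plan could not recover a Visit 4 result that was never assayed.

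**Working it through.** **Inputs.** Three-draw subjects per group: 160 (Section 5.1.1). Subset A ~70 and Subset B ~90 (Table 5.1); 70 + 90 = 160, so the plan's own counts agree. rSBA set: 100 per group (Section 9.2.2.2). The protocol states no number of Visit 4 rSBA results, so there is no figure of its own to reproduce.

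**Step 1: Visit 4 and Visit 2 counts under each reading.**

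- Enrolment order: all 70 of Subset A enter first, leaving 100 − 70 = 30 from Subset B. This is also the smallest Subset B count that any 100 of the 160 can contain.
- Membership randomized over all 160: the number from Subset B is hypergeometric (160 in total, 90 in B, 100 drawn). Mean 100 × 90/160 = 56.25; 2.5th to 97.5th percentile 50 to 62. Subset A has mean 100 × 70/160 = 43.75, range 38 to 50.

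**Step 2: precision of a percentage** (Clopper-Pearson, the method in Section 12.1.2.2). The rates near 50% and 90% are assumed for illustration.

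| Time point and reading | Count | 95% interval (%) | Width (points) |
|---|---|---|---|
| Visit 4, order | 15/30 | 31.3 to 68.7 | 37.4 |
| Visit 4, randomized | 28/56 | 36.3 to 63.7 | 27.3 |
| Visit 4, order | 27/30 | 73.5 to 97.9 | 24.4 |
| Visit 4, randomized | 50/56 | 78.1 to 96.0 | 17.8 |
| Visit 2, order | 35/70 | 37.8 to 62.2 | 24.4 |
| Visit 2, randomized | 22/44 | 34.6 to 65.4 | 30.9 |

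**Step 3: precision of a GMT.** The half-width on the log scale, in SD units, is t(0.975, n−1)/√n.

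- Visit 4: 0.373 at n = 30 and 0.268 at n = 56. Ratio 1.39, so the interval is about 39% wider under the order reading.
- Visit 2: 0.304 at n = 44 and 0.238 at n = 70. Ratio 1.28, so the interval is about 28% wider under the randomized reading.

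**Step 4: attrition.** These are scheduled samples. If the 30% non-adherence of Section 12.5 is assumed to apply to this set, 30 × 0.7 = 21 and 56.25 × 0.7 = 39.4. The contrast between the readings keeps the same ratio.

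**Step 5: which reading the text supports.** The order words appear only in the two Table 5.1 footnotes. Those footnotes also say that the subjects are randomized to the visit pattern. The legend beneath them and the procedure-table footnotes use randomized with no order, and Sections 5.1.1 and 7 state no order. The balance favours randomized membership, although no sentence settles it.

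**The case for a change.** The best argument for acting is that the ambiguity lies in the section the protocol itself names as the definition, that the order reading gives the fewest Visit 4 results possible, and that clarifying it would cost one sentence. Persistence is also a stated aim in Section 5.1.2, and dose-2 rSBA seroresponse needs both a Visit 4 and a Visit 5 serum, so the full 100 at Visit 5 do not help. The order words are real, the arithmetic is correct, and the pairing does depend on Visit 4.

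It does not establish an error in the rSBA rule. If membership is randomized, the rule stands as written and the clarifying sentence alters no result. If membership is sequential, re-selecting about 44 from A and 56 from B narrows the Visit 4 interval near 50% from 37.4 to 27.3 points but widens the Visit 2 interval from 24.4 to 30.9. Visit 2 supports the dose-1 rSBA baseline, fold rise and seroresponse, which also belong to Secondary Objective 2. The protocol sets no A:B ratio and no precision target for rSBA, so it gives no ground for preferring either time point.

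The figure of 56 is itself conditional on all 160 being exchangeable. Section 12.5 adds 100 subjects because of COVID-19. At 2:2:1, Group 3's share is 100 × 1/5 = 20, which implies 140 before. The text still calls both subsets approximately half. One may infer, though it is not stated, a 70:70 split with later subjects added to B. The first 100 of those 140 would contain 100 × 70/140 = 50 from B on average.

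For persistence alone, Groups 1 and 2 have the same vaccine schedule up to the Visit 4 draw. Pooling them under the order reading would give 60 subjects and a width of 26.4 points near 50% (30/60). The protocol plans no such pooling, and it would not help dose-2 seroresponse by group.

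**Conclusion.** No change to the plan is needed. The Table 5.1 footnotes are loosely worded, and the rest of the text points to randomized subsets. On that reading, with all 160 exchangeable, the rSBA rule gives about 56 Visit 4 and 44 Visit 2 samples per group before attrition. That is close to the cohort's own balance.

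On the less favoured order reading the counts are 30 and 70. This gives up about 10 points of interval width near 50% at Visit 4 (37.4 − 27.3 = 10.1) and gains about 6.5 at Visit 2 (30.9 − 24.4). That is a trade-off between two descriptive time points, and the protocol ranks neither.

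The primary hSBA comparison at Visit 5 and its power, every hSBA analysis (about 90 scheduled per group at Visit 4), and the Visit 5 rSBA GMTs and threshold rates (about 100 per group) are the same on either reading. The conclusion rests on the protocol alone. The detailed allocation procedures, which Section 6.5 places in the Operating Guidelines, could not be checked.
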